5.2.2. Patient Selection

All patients who underwent colonoscopy, agreed to use EndoAngel and generally meet the study requirements were screened based on the inclusion/exclusion criteria. Patients who passed the screening were enrolled and recorded in the subject screening and enrollment tables. There is no bias in the choice of the enrolled subjects. The date of screening, the results (enrolled or not), and the primary reason for not selecting subjects (such as not meeting inclusion criteria, or not interested in participating in the study) will be recorded.

After the patients are enrolled, the research center should complete the preoperative study data collection.

It is desirable to be able to collect complete data for all enrolled patients, without those withdrawal from the study.

5.2.3. Subject identification number

Patients were numbered after signing informed consent.

The subject number begins with EA as a fixed number and is numbered starting from 0001 at the time of signing the informed consent. For example, the first patient who signed the informed consent was EA0001, and the second one was EA0002.

Once the subject identification number is assigned, the number is not reusable.

5.3. Treatment Description

This section applies to individuals who have signed an approved informed consent and have been identified as eligible to participate in this study on the basis of the inclusion and exclusion criteria. This section introduces the preoperative, surgical and postoperative management of subjects in detail.

5.3.1. Patient Screening Assessments

- 1) History
- 2) Physical examination
- 3) Hematuria pregnancy test (if required)

5.3.2. Pre-Procedure Managements

- 1) Fasting for 14 hours and water deprivation for 2 hours before examination
- 2) Routine bowel preparation.
- 3) Psychological counseling.
- 4) Performing routine anesthesia for painless enteroscopy patients.

[figure not shown]
5.3.3. Intraoperative Managements

- 1) Patient position: lateral position with appropriate restraint.
- 2) Insertion route: according to the actual situation of the subject, usually through the anus
- 3) Routine observation

5.3.4. Post-operative Managements

- 1) Postoperative routine nursing
- 2) Subjects were observed to wake up
- 3) Patients without polyps and other lesions were followed up until the patient woke up and left the endoscopic room.
- 4) Patients with polyps and other lesions detected but no biopsy was taken during the operation should be followed up until the patient received polypectomy and other treatments, and the follow-up period should be within 7 days after the colonoscopy.
- 5) Record complications (if any).

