Expected effect:	ENDOANGEL's intended use is to assist doctors in identifying patients who require a second colonoscopy, thus avoiding missed adenomas and excessive washing time costs due to subjective factors and poor decision-making. It can improve the quality of endoscopy and the detection rate of digestive tract lesions.
Primary Endpoint:	1. Adenoma detection rate (ADR); 2. Boston Bowel Preparation Score of intestinal segment in artificial intelligence system;
Secondary Endpoints:	1. Polyp detection rate (PDR); 2. Mean number of adenomas per procedure (MAP); 3. Mean number of polyps per procedure (MNP); 4. The detection rate of large, small and micro - small adenoma and the average number of detection; 5. The detection rate and average number of polyps in large, small and micro-sized polyps; 6. Adenoma detection rate (ADR) of different location 7. Mean number of adenomas per procedure (MAP) of different location 8. Scope-forward time; 9. withdrawal time; 10. Cecal intubation rate; 11. Boston Bowel Preparation Score of endoscopists;
Trail design:	prospective, single group, observational, single-centre
Participants:	Male and female subjects aged 18 years or older will require a colonoscopy, and voluntarily provide endoscopic imaging data and sign an informed consent form.
Sample size:	200 samples were collected to explore the sample distribution, and then calculate the sample size according to the sample distribution.
Study Process:	Subjects who met all inclusion criteria and did not meet all exclusion criteria were included in the study before colonoscopy. During the colonoscopy, the endoscopists need to remain in the same without withdrawal while flushing the bowel. The biopsied patients are followed up for one week. the non-biopsied patients are followed up at the end of their colonoscopy , and the results are sent to an independent data analysis team for review. We will collect the patients' video and exclude the clips of irrigation, biopsy, and

[figure not shown]

	observation of polyp. Then the EndoAngel evaluates the Boston Bowel Preparation Scale of the ascending colon, transverse colon and descending colon, and calculates the proportion of 1 Score.
Security	Safety incidents shall be evaluated and reported according to the quality management measures for clinical trials of medical devices

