1.1. Time and Event Tables

Events	Screening period (d -30~ -1)	The day of colonoscopy (d 0)	Follow up (d 1-14)
Informed Consent	X		
Basic characteristics	X		
Medical history/surgical history	X		
Inclusion/Exclusion Criteria	X		
Colonoscopy		X	
Concomitant treatment	X	X	
Concomitant medication	X	X	
Adverse Events		X	X
Research completed			X

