1.2. Flow chat

Follow-up Time: The biopsied patients are followed up for one week. the non-biopsied patients are followed up at the end of the study

2. Introduction

Colorectal disease as a common human disease seriously affects the health of human life. With the aging of the population, the change of diet structure and the aggravation of environmental pollution, the incidence of colorectal diseases, such as colon cancer, Colon Polyp and inflammatory bowel disease, has gradually increased¹⁻².

Colonoscopy is the simplest and most widely available screening procedure for colorectal cancer(CRC) prevention and early detection². Colonoscopy can clearly observe the small changes in the terminal ileum and the colorectal, such as erosion, ulcers, bleeding, congestion, edema, polyps, early cancer, and so on. Colonoscopy can biopsy the lesion site for pathological examination, to histologically qualitative the characterization of mucosal lesions, such as inflammation, polyp nature, the degree of differentiation of cancer, and so on. It is helpful to understand the severity of the lesion and guide the formulation of the correct treatment plan or judgment of treatment effect. Colonoscopy can also be the minimally invasive endoscopic treatment of colorectal polyps, early cancer, bleeding, foreign bodies and other diseases.

Because the quality of bowel preparation affects the colonoscopy's ability to detect adenomas and polyps, adequate bowel preparation is necessary to ensure optimal use of colonoscopy in CRC prevention³. Almost all clinical guidelines recommend adequate bowel preparation before colonoscopy⁴⁻⁶. However, up to one third of colonoscopies have been found to show inadequate bowel preparation, which is estimated to increase the cost of colonoscopies by 12% to 22%. And there are 20% of patients' bowel is not adequately prepared. When the patient's bowel preparation is inadequate, the difficulty of flushing may lead to missed detection of adenomas⁷⁻⁹. so doctors need to accurately identify such patients and tell them to have a second colonoscopy after a full bowel cleanse¹⁰. However, the evaluation of intestinal cleanliness is decided by doctors subjectively, and there is no objective and effective scoring standard to guide the patients to accept the second colonoscopy.

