3.1. Primary Endpoint

- 1) The adenoma detection rate (ADR):

ADR was calculated by dividing the total number of patients being detected adenomas by the number of colonoscopies.

- 2) Cleanliness assessment of different intestinal segment in the artificial intelligence system
The artificial intelligence system evaluates the Boston Bowel Preparation score of the ascending colon, transverse colon and descending colon in real-time, and calculates the proportion of 1 Score

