5.1. Summary of Study Process

- If the patient meets the inclusion criteria, the patient is invited to participate in the study and then the informed consent procedure for the clinical trial is applied.
- Assess patients' eligibility based on the inclusion/exclusion criteria.
- If the patient meets the inclusion/exclusion criteria, information prior to endoscopy will be collected.
- A colonoscopy is performed after informed consent. Any intraoperative adverse events are recorded on the CRF for submission and subsequent analysis.
- Follow-up will be performed from the postoperative to the study completion, as detailed in the time and event table.

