5.3.5. Specimen handling procedure

5.4. Suspension and withdrawal

Patients who were screened and confirmed to be eligible for the study, signed the informed

consent and completed the randomization were considered as enrolled. If serious program deviation, withdrawal, or death occurs, the subject study is considered to be suspended. If the subject discontinues the study after obtaining informed consent, the data before the discontinuation will still be included in the study-related analysis.

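### Do the conflicting follow-up statements for non-biopsied patients leave the adenoma detection rate without a usable counting rule?

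*Combined protocol and SAP*

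**What the plan says.** The document describes follow-up of non-biopsied patients in several places.

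- Synopsis, Study Process: "the non-biopsied patients are followed up at the end of their colonoscopy".
- Section 1.2: "the non-biopsied patients are followed up at the end of the study".
- Section 5.3.4, item 3: "Patients without polyps and other lesions were followed up until the patient woke up and left the endoscopic room".
- Section 5.3.4, item 4: for a polyp seen but not biopsied, follow-up lasts until polypectomy or other treatment, and "the follow-up period should be within 7 days after the colonoscopy".
- Section 5.1: "Follow-up will be performed from the postoperative to the study completion, as detailed in the time and event table". The table in section 1.1 has one column, "Follow up (d 1-14)", not split by biopsy status.

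On the endpoint, section 3.1 says "ADR was calculated by dividing the total number of patients being detected adenomas by the number of colonoscopies". Section 3.2 defines the mean number of adenomas (MAP), the polyp detection rate (PDR) and the mean number of polyps (MNP) in the same style, with adenomas and polyps kept apart. None of these definitions mentions histology. Heading 5.3.5, "Specimen handling procedure", has no text beneath it in the supplied copy, and the case report form cited in section 6.1 was not supplied.

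**The concern.** ADR is a primary endpoint and, under sections 7.3 and 7.4, the outcome of the planned curve against the share of score 1. Section 5.3.4 item 4 shows that the protocol expects some polyps to leave the index procedure without tissue. If outcome collection closed with the colonoscopy or at 7 days, a patient whose only adenoma was removed later would have no histology yet stay in the denominator.

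Counting such patients as negative would understate ADR and MAP; counting them as positive could overstate both. If the unresolved share varied with cleanliness, the curve itself would be distorted, in a direction set by the counting rule. Section 7 contains no missing-data rule, so the choice could in principle be made after seeing the data.

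**Working it through.** **1. The follow-up statements by type of patient**

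| Patient | Synopsis | Section 1.2 | Section 5.3.4 |
|---|---|---|---|
| Biopsied | one week | one week | not addressed |
| No lesion | end of colonoscopy | end of study | until leaving the room |
| Polyp, not biopsied | end of colonoscopy | end of study | until polypectomy, within 7 days |

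The third row holds three statements that cannot all apply. In the second row, section 1.2 disagrees with the other two. The table in section 1.1 adds little conflict, because 7 days fits inside days 1-14 and section 5.1 defers to that table.

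**2. Does any of these windows close the collection of histology?**

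In section 1.1 the follow-up column is marked only for adverse events and study completion. Section 5.3.4 sits with nursing, waking and complications. The synopsis mentions follow-up and the sending of results to the analysis team in one sentence, so a link is possible, but it sets no pathology cut-off. Item 4 can also be read as expecting polypectomy inside the week, which would supply the missing tissue.

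**3. What do the definitions give when read literally?**

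A polyp not shown to be an adenoma enters PDR and MNP (section 3.2) and does not enter ADR (section 3.1) or MAP (section 3.2). The introduction describes pathological examination of a biopsy as the way polyp nature is established. That is background, not an endpoint definition, but it points the same way.

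**4. Size for ADR itself**

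The plan has no figure to reproduce: 200 (section 7.4) is a chosen exploratory number with no stated error rate, power or effect. From the documents: N = 200, and 20% inadequately prepared (introduction, background figure), so 0.20 × 200 = 40.

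- Shift per affected patient: 1/200 = 0.5 points overall; 1/40 = 2.5 points among 40 poorly prepared colons.
- Assumed confirmed ADR 25%, and u = share of patients whose only possible adenoma lacks histology:

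| u | as non-adenoma | as adenoma, 25 + u | dropped, 25/(1 − u) |
|---|---|---|---|
| 2% (4 patients) | 25.0% | 27.0% | 25.5% |
| 5% (10) | 25.0% | 30.0% | 26.3% |
| 10% (20) | 25.0% | 35.0% | 27.8% |

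The 95% half-width is 1.96 × √(0.25 × 0.75/200) = 6.0 points. The widest choice of rule matches sampling error only when u is near 6%.

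**5. Size for the curve**

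Simplification: two groups, 20% poorly prepared, pooled two-proportion z test at two-sided 5%, exact binomial enumeration. Assumed true ADR is 30% in both groups. With unresolved polyps counted as negative, observed ADR = 0.30 × (1 − unresolved share).

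| Unresolved, clean vs poor | Observed ADR | Rejection, N = 200 | N = 1000 (assumed) |
|---|---|---|---|
| 20% vs 20% | 24.0 vs 24.0% | 5.1% | 5.0% |
| 5% vs 10% | 28.5 vs 27.0% | 5.2% | 6.7% |
| 5% vs 20% | 28.5 vs 24.0% | 7.9% | 24.0% |
| 5% vs 30% | 28.5 vs 21.0% | 14.7% | 57.9% |
| 30% vs 5% | 21.0 vs 28.5% | 19.0% | 61.2% |

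Counted as adenoma, with an assumed 20% of patients having only non-adenomatous polyps, 5% vs 30% gives 0.30 + 0.20 × 0.05 = 31% against 0.30 + 0.20 × 0.30 = 36%, the opposite sign.

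With an equal 20% unresolved and counted as negative, a true 30% vs 20% shrinks to 24% vs 16%, and power at N = 200 falls from 23.1% to 17.5%.

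The answer also depends on the model. If *confirmed* ADR, not true ADR, is equal across cleanliness, counting unresolved polyps as negative creates no difference at all.

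**The case for a change.** The strongest case for a change is that the contradiction is in current text, that section 5.3.4 item 4 itself anticipates unsampled polyps, and that it does not say what happens when polypectomy comes after 7 days. Excluding patients with a contraindication for biopsy (section 2.2) removes only one source of these. The outcome feeds a curve meant to guide decisions on a second colonoscopy, and a counting rule chosen late could change its slope. A clarifying sentence and a count of polyps without histology by cleanliness level would cost little.

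The textual part stands. The follow-up statements conflict, and no supplied text names histology as the reference standard, says whether later polypectomy pathology counts toward the index colonoscopy, or classifies a polyp never examined. The arithmetic also reproduces.

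What does not stand is the step from there to a biased ADR. It needs the follow-up window to close pathology collection, which the documents do not say. The reversal of sign needs unconfirmed polyps to be counted as adenomas, which is the less natural reading of sections 3.1 and 3.2. The large error rates need both an assumed sample of 1000 and a 25-point gap in unresolved histology, while at 200 the plan names no test. The missing rule may also sit under heading 5.3.5 or in the case report form.

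**Conclusion.** No change to the endpoint, the analysis or the sample size follows. The follow-up conflict is a clerical inconsistency: the synopsis, section 1.2 and section 5.3.4 must be reconciled, and this review takes no view on which follow-up rule is right. The unwritten histology rule is a missing detail that analysts can fill sensibly by taking adenoma to mean confirmed adenoma, with unconfirmed polyps left in the polyp endpoints. Stating that convention and the number of polyps without histology when reporting is ordinary good practice.

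The effect is of unknown size: 0.5 points of ADR per affected patient at N = 200, near nominal error for a small gap in unresolved histology, and large only with a much bigger sample and a wide gap. Apart from the 200 and the background 20%, every input to those error rates (ADR, unresolved shares, the final sample, the two-group test) is an assumption. A pathology cut-off or a contrary counting rule under heading 5.3.5 or in the case report form would reopen the question.

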5.3.5. Specimen handling procedure

5.4. Suspension and withdrawal

Patients who were screened and confirmed to be eligible for the study, signed the informed

consent and completed the randomization were considered as enrolled. If serious program deviation, withdrawal, or death occurs, the subject study is considered to be suspended. If the subject discontinues the study after obtaining informed consent, the data before the discontinuation will still be included in the study-related analysis.

5.4.1. Pre-Procedure

In any time during the study period, even before colonoscopy, participants could withdraw their informed consent whenever necessary. Researchers can withdraw participants before surgery according to safety considerations in the inclusion and exclusion criteria.

5.4.2. Intraprocedure

For safety reasons, the investigator may have the subject quit during the procedure. For example, the patient is not suitable for receiving the instrument for the study or the endoscopists do not use the specified instrument for any reason. If the following serious cases occur, please withdraw during the operation:

- 1) Perforation
- 2) Bleeding
- 3) Allergy to narcotic drugs
- 4) Poor intestinal cleanliness
- 5) Unable to complete colonoscopy due to obstruction or other reasons

5.4.3. Replacement

Subject will be deemed to have commenced the study upon completion of the informed consent process, and any subject who has been discontinued prior to or during the endoscopic examination will not subsequently be replaced by other subjects.

5.5. Concomitant therapy and medication

The concomitant treatment and concomitant medication were recorded from the time the subject signed the informed consent to the time the study was completed. Concomitant treatment and concomitant medication should be recorded in the CRF, or a clear copy of the form available from the research center should be kept in the CRF as research data to identify other factors affecting the end of the study. When recording the concomitant treatment and concomitant medication, the indications and the starting and ending time of use should be clearly defined, and the corresponding types of adverse events should be indicated for the treatment measures to cope with adverse events. When using a copy of the study center form, the investigator should sign the copy and indicate the date of review to confirm that the document is a study document.

6. Basis of study protocol and risk/benefit analysis

EndoAngel is used to provide assistant to monitor the operation of endoscopists, which will not provide diagnosis. Doctors make their own diagnosis on the basis of EndoAngel's results. The security of the software and the improvement of endoscopic physician's diagnosis and treatment level have also been confirmed in the previous feasibility study. And the patients in this study carry out the diagnosis and treatment according to the conventional treatment measures, which are formulated in accordance with the standard medical treatment procedures and do not increase the risk of the subjects.

6.1. Selection of endpoints

The primary outcome of the study are the adenoma detection rate (ADR) and Cleanliness assessment of different intestinal segment in artificial intelligence system.

The secondary outcomes of this study were: 1.Polyp detection rate (PDR);2.Mean number of adenomas per procedure (MAP); 3.Mean number of polyps per procedure (MNP);4.The detection rate of large, small and micro - small adenoma and the average number of detection;5.The detection rate and average number of polyps in large, small and microsized polyps;6.Adenoma detection rate (ADR) of different location;7.Mean number of adenomas per procedure (MAP) of different location;8.Scope-forward time;9.withdrawal time;10.Cecal intubation rate;11.Boston Bowel Preparation Score of endoscopists;

Adverse events in safety indicators shall be judged in accordance with relevant regulations, and serious adverse events shall be recorded and reported in accordance with regulations.

Other evaluations are detailed in the Case Report Form (CRF).

6.2. Definition of participants

Patients were included according to the indications and contraindications described in the use plan. Because of practical reasons (such as younger patients, participation in a number of clinical studies, alcohol/drug dependence patients, and other factors that may affect the completion and/or reliability of gastroscopy) and ethical reasons (whether informed consent can be completed, etc.), the entry and discharge criteria have been reduced.

6.3. Adverse events

The relevant definitions of adverse events are as follows:

Adverse Events (AE): Any adverse medical event, unexpected disease or injury, or adverse clinical manifestations (including abnormal laboratory findings) that occur in a subject, user or other person, whether or not associated with medical devices.

Serious Adverse Events (SAE): Adverse Events with the following information:

- causing death.
- leading to severe deterioration of the health of the subjects, including
- leading to life-threatening diseases or injuries,
- Causing impairment of body structure or function.
- Need hospitalization or extended hospitalization
- lead to hospitalization and preventive medical or surgical intervention
- Permanent damage to body structure or function
- Fetal distress, fetal death or congenital abnormalities or congenital defects.

Note: Hospitalization for existing conditions, or surgery required in the program, without serious deterioration of health status, is not considered a serious adverse event. Purposeful hospitalization, such as economic or reimbursement reasons, is not considered a serious adverse event.

Unexpected adverse device response (UADE): refers to adverse events related to medical devices that were not previously identified in the current version of the risk analysis report in terms of nature, severity or incidence. The definition includes any event caused by insufficient or inadequate description of the use or deployment of the device. This definition includes any event caused by a user's error.

6.4. Expected and trial-related adverse events

Previous studies have shown that the expected adverse events are basically the same as the complications of conventional endoscopic diagnosis and treatment.

The instrument used in this experiment is a medical software which is not in contact with human body. There is no difference between the experimental operation and the routine operation. The intervention measures (such as randomized process) in the experiment may slightly increase the incidents of diagnosis and treatment.

